5.3.3. Sequence of Study Drug Administration

The intermittent weekly dosing sequence for nanatinostat in combination with valganciclovir in Phase 1b dose levels 1 through 3 (defined in Table 4) is presented in Figure 6.

For patients receiving divided dosing of nanatinostat and single dosing of valganciclovir (dose levels 4 and 5 defined in Table 4), the first dose of nanatinostat and the only dose of valganciclovir will be taken at approximately breakfast time; the second dose of nanatinostat 4 hours later will be taken at approximately lunch time. The sequence for intermittent divided dosing of nanatinostat only is presented in Figure 7.

For the first 21 days of Cycle 1, patients receiving divided dosing of both nanatinostat and valganciclovir (dose levels 6 and 7 defined in Table 4) will take the first dose of nanatinostat and valganciclovir at approximately breakfast time, the second dose of nanatinostat 4 hours later at approximately lunch time, and then the second dose of valganciclovir in the evening at approximately dinner time on Days 1 to 4 per week. Patients will continue to receive divided dosing of valganciclovir at breakfast and dinner on Days 5 to 7 per week. Following the first 21 days, these patients will continue to receive divided dosing of nanatinostat on Days 1 to 4 per week, but subsequent valganciclovir dosing will be reduced to once daily at breakfast. The sequence for divided dosing of both nanatinostat and valganciclovir is presented in Figure 8.

For patients receiving split daily dosing of both nanatinostat and valganciclovir (dose levels 8 through 13 defined in Table 4), the first dose of nanatinostat and valganciclovir will be taken at approximately breakfast time and the second dose of nanatinostat and valganciclovir will be taken 4 hours later at approximately lunch time on Days 1 to 7. The sequence for split daily dosing of both nanatinostat and valganciclovir is presented in Figure 9.

The dosing sequence for nanatinostat and valganciclovir during the two dose optimization cohorts following identification of the RP2D is presented in Figure 10.

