5.5. Dose Escalation Guidelines

5.5.1. Provisional Dose Levels

Table 4 describes the starting doses and the provisional dose levels of nanatinostat and valganciclovir (Phase 1b) and nanatinostat and valganciclovir with pembrolizumab (Phase 2 Dose Optimization and Phase 2 Expansion) to be evaluated. The actual dose levels will be determined based on available data following a discussion with Investigators during dose-escalation teleconferences. No intrapatient dose escalation will be permitted in the Phase 1b dose escalation.

Table 4: Phase 1b: Dose Levels – Nanatinostat and Valganciclovir

Dose Level	Nanatinostat Oral Dose on Days 1-4/Week	Valganciclovir Oral Dose Daily
-1	10 mg once daily	900 mg once daily
1	20 mg once daily	900 mg once daily
2	30 mg once daily	900 mg once daily
3	40 mg once daily	900 mg once daily
4	20 mg and 10 mg divided dose	900 mg once daily
5	20 mg twice daily	900 mg once daily
6	10 mg twice daily	900 mg twice daily × 21 days, then once daily
7	20 mg and 10 mg divided dose	900 mg twice daily × 21 days, then once daily
	Nanatinostat Oral Dose Twice Daily on Days 1-7/Week	Valganciclovir Oral Dose Twice Daily on Days 1-7/Week
8 ^a	20 mg and 10 mg divided dose	450 mg twice daily

9ª	20 mg and 20 mg divided dose 450 mg twice daily			
10 ^a	30 mg and 20 mg divided dose	450 mg twice daily		
11ª	30 mg and 30 mg divided dose	450 mg twice daily		
12ª	40 mg and 30 mg divided dose	450 mg twice daily		
13ª	40 mg and 40 mg divided dose	450 mg twice daily		

DLT = dose-limiting toxicity; RP2D = recommended Phase 2 dose

Guidelines for Dose Escalation 5.5.2.

During the DLT evaluation window of both phases of the study, patients who permanently discontinue study treatment prior to receiving 75% of the planned number of nanatinostat and valganciclovir doses or 2 pembrolizumab doses due to reasons other than study drug-related toxicity will not be considered evaluable for DLT and may be replaced.

Phase 1b

IND 154400

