8.8. Reporting of Overdose

An overdose is defined as any accidental or intentional use of the study drug in an amount higher than the protocol-defined dose.

If an overdose occurs, whether accidental or intentional, and is associated with an AE, the AE (not the overdose) should be recorded on the Adverse Event eCRF. If an overdose occurs, with or without an AE, the additional doses taken will be recorded on the dosing eCRF. Adverse events associated with overdose, misuse, abuse, or medication error should be reported using the procedures detailed in Reporting of Serious Adverse Events (Section 8.2) even if the AEs do not meet seriousness criteria.

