4.5.2 Measurements of Treatment Compliance

Compliance with both nanatinostat and valganciclovir will be determined as the total number of tablets taken divided by the expected number of tablets taken, multiplied by 100.

The expected number of tablets administered will be determined using the prescribed dosing information contained in Table 4 of the clinical study protocol, where nanatinostat and valganciclovir are dispensed in 10 mg and 450 mg tablets, respectively. The number of tablets expected will be calculated for each cycle and then multiplied by the number of cycles the patient completes.

The total number of tablets taken will be determined using the data recorded on the Study Drug Exposure eCRF pages for nanatinostat and valganciclovir. If a patient is administered study drug as expected (with no changes to dose administered, no interruptions, delays, or missed doses), then the Study Drug Exposure eCRFs will include a record for that cycle that indicates “No Change to Dose.” In this case, the total number of tablets taken in each cycle will be calculated as the number of days in the cycle where the doses were administered (multiplied by two if a divided dose). Missed doses are recorded on the Study Drug Exposure eCRFs as “Missed/Dosing Error.” When calculating the number of missed doses, if a patient reports “Missed/Dosing Error” on the eCRF, it will be assumed no study drug was administered on that date.

Compliance with pembrolizumab will be determined as the total number of infusions received divided by the number of expected infusions, multiplied by 100. The number of expected infusions will be determined using the dosing schedule provided in Figure 10 of the clinical study protocol. The total number of infusions received will be determined using the *Study Drug Administration Log - Pembrolizumab* eCRF.

Dosing compliance will be summarized using descriptive statistics, for each dosing regimen based on the Safety Analysis Population. The number and percentages of patients who are <80% compliant and $\geq 80\%$ compliant within each dosing regimen will be summarized. Treatment compliance will also be included in a by-patient data listing.

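### Scoring every Missed/Dosing Error date as no drug taken understates compliance on divided-dose regimens when only the second dose was missed

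*SAP*

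**What the plan says.** SAP 4.5.2 defines compliance for nanatinostat and valganciclovir as the "total number of tablets taken divided by the expected number of tablets taken, multiplied by 100". Expected tablets are worked out per cycle from Protocol Table 4 and multiplied by the number of cycles the patient completes. For cycles given as planned, the number of dosing days is "multiplied by two if a divided dose", so the section recognises two intakes in a day.

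On departures from the plan, it says "Missed doses are recorded on the Study Drug Exposure eCRFs as" Missed/Dosing Error. When that code appears, "it will be assumed no study drug was administered on that date". No exception is made for divided regimens. The results are summarised by dosing regimen, including "The number and percentages of patients who are <80% compliant and" those at 80% or more.

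Protocol 5.3.3 and Table 4 (Section 5.5.1) describe two intakes a day on most dose levels. At levels 8-13, "the second dose of nanatinostat and valganciclovir will be taken 4 hours later at approximately lunch time on Days 1 to 7". Level 9, for example, is "20 mg and 20 mg divided dose 450 mg twice daily". Nanatinostat is divided at levels 4-13. Valganciclovir is taken twice daily at levels 8-13, and at levels 6-7 for the first 21 days.

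**The concern.** The measure is built on tablets, but the missed-dose rule works on whole dates. On a once-daily regimen the two agree, because one missed dose is one missed day. On a divided regimen they disagree whenever the first dose was taken and the second was not: the tablets swallowed at breakfast are credited as nothing.

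The error therefore depends on the regimen, and the table is laid out by regimen. Patients with the same habit of missing single doses would look less adherent on divided dosing, and some would fall on the wrong side of the 80% line. SAP 4.8 says enrollment stopped after the final Phase 1b dose level was completed. The Phase 1b dose levels, most of them divided, are therefore the data to be reported.

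**Working it through.** The documents give no compliance figure that uses this rule, so there is nothing to reproduce. The check is tablet arithmetic.

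**Inputs**
- Tablet strengths: nanatinostat 10 mg, valganciclovir 450 mg (SAP 4.5.2).
- Cycle lengths: 28 days for Cycle 1, 21 days afterwards (Protocol 3.1.2).
- Doses: Protocol Table 4. Cut-off: 80% (SAP 4.5.2).

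**Notation.** D is the number of dosing days in the completed cycles, a and b are the tablets in the first and second dose, and k is the number of days on which only the second dose was missed. All other doses are taken and counted in tablets, and each drug is scored from its own records.

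**Formulas**
- SAP rule: 1 - k/D
- Tablets actually taken: 1 - k·b/[D(a+b)]
- Overcharge per missed second dose: (a+b)/b

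**Overcharge.** For equal doses it is 2. For nanatinostat 20 + 10 mg (2 + 1 tablets; levels 4, 7 and 8) it is 3/1 = 3. On once-daily dosing a missed dose removes the whole day under both counts, so the overcharge factor is 1.

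**Where the 80% line is crossed**

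| Regimen and completed cycles | D | Days k misclassified | SAP rule, first to last k | Actual, first to last k |
|---|---|---|---|---|
| Equal doses, daily, Cycle 1 only | 28 | 6-11 | 22/28 = 78.6% to 17/28 = 60.7% | 50/56 = 89.3% to 45/56 = 80.4% |
| Equal doses, daily, Cycles 1-2 | 49 | 10-19 | 39/49 = 79.6% to 30/49 = 61.2% | 88/98 = 89.8% to 79/98 = 80.6% |
| Nanatinostat 20 + 10 mg, daily (level 8), Cycle 1 only | 28 | 6-16 | 22/28 = 78.6% to 12/28 = 42.9% | 78/84 = 92.9% to 68/84 = 81.0% |
| Nanatinostat 20 + 20 mg, Days 1-4 (level 5), Cycle 1 only | 16 | 4-6 | 12/16 = 75.0% to 10/16 = 62.5% | 56/64 = 87.5% to 52/64 = 81.25% |

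The equal-dose rows apply to nanatinostat at levels 9, 11 and 13 and to valganciclovir at levels 8-13. With equal doses the rule drops a patient below 80% once k exceeds 20% of dosing days. Counted in tablets, that takes more than 40%.

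**The case against.** Several limits are real.

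**Completed cycles.** A reader might apply the arithmetic to one 21-day cycle, where five half-missed days would score 16/21 = 76.2%. The SAP does not compute compliance that way. A patient who has completed a 21-day cycle has also had the 28-day Cycle 1, so five such days score 44/49 = 89.8% (93/98 = 94.9% by tablets), on the right side of the line. Misclassification needs partial misses on more than a fifth of all dosing days, and the documents give no rate for these.

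**Missed first doses.** Protocol 5.6.3 tells patients at levels 4-13 to resume the planned schedule the following day after a missed dose. If breakfast is missed and lunch is then skipped, a zero day is correct. That does not cover the case where breakfast was taken and only lunch was missed.

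**Overdoses.** A reader might infer from the code's name that a day of excess intake is also scored as zero. Protocol 8.8 says "If an overdose occurs, with or without an AE, the additional doses taken will be recorded on the dosing eCRF" but names no category, and SAP 4.5.2 introduces the zero rule as part of counting missed doses. If dosing errors with partial or excess intake are entered under this code, those days would be mis-scored on any regimen, once-daily included. The documents do not confirm that they are. The confinement of the error to divided regimens therefore holds for missed doses only.

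**Consequences.** A reader might infer that the table could have steered the choice of RP2D. Protocol 5.5.2 and the footnote to Table 5 base that choice on DLTs, adverse events, tolerability, PK, antitumor activity and plasma EBV DNA. DLT evaluability has its own rule, based on 75% of planned doses. No analysis set in SAP 4.2 uses compliance, SAP 4.1.1 plans no formal comparison of regimens, and SAP 4.8 says the RP2D had already been determined.

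**Source data.** The eCRF layout is not shown, so dose-by-dose intake may not be available for every date. That argues for a fallback, not for zeroing every date. Protocol 5.6 requires all doses to be recorded in the eCRFs, and Protocol 5.9.3.1 has paper diaries record doses and collect tablet counts.

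**Conclusion.** The concern holds in this form. The date-level rule contradicts the SAP's own tablet-based measure on divided regimens. When the second dose is missed after the first was taken, the loss is overstated twofold for equal doses and threefold for nanatinostat 20 + 10 mg. Missed once-daily doses are charged correctly, so the by-regimen compliance summary and the 80% split are biased against divided dosing.

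How often patients would be misclassified cannot be stated, because it depends on a frequency of partial misses that the documents do not give. The ranges above assume that only second doses were missed and that every other day was counted correctly in tablets. How SAP 4.5.2 counts tablets in cycles with no dose change is a separate question and is set aside here.

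The effect stays within descriptive compliance outputs, so this is a change that should be made and not a threat to the trial's conclusions.

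**What to change.** Replace the sentence in SAP 4.5.2 with:

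> For a date recorded as Missed/Dosing Error, tablets taken are those recorded as taken on that date; a missed single dose of a divided regimen removes only that dose's tablets. The date is set to zero only if no dose was taken or the record does not allow the dose taken to be determined, and the number of such dates is reported.

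This keeps the present convention as a fallback and shows how often it was used. If partial or excess intake does turn out to be entered under the code, the same wording scores it at the recorded amount.

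The cost is one change of SAP text, some programming and possibly some data queries to establish which dose was missed. Dosing instructions are unaffected.

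### SAP 4.5.2 divides a count of doses by a count of tablets, so as written a fully adherent patient scores below 100% wherever a dose is more than one tablet

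*SAP*

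**What the plan says.** SAP 4.5.2 defines compliance for nanatinostat and valganciclovir as the percentage ratio of tablets taken to tablets expected.

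- **Expected.** The count comes from the doses in Protocol Table 4, "where nanatinostat and valganciclovir are dispensed in 10 mg and 450 mg tablets, respectively". For scope, "The number of tablets expected will be calculated for each cycle and then multiplied by the number of cycles the patient completes".
- **Taken, no dose change.** Where the eCRF records *No Change to Dose* for a cycle, tablets taken is the "number of days in the cycle where the doses were administered (multiplied by two if a divided dose"). No formula is given for a cycle in which the dose was modified.
- **Taken, missed dose.** Where the eCRF records *Missed/Dosing Error*, "it will be assumed no study drug was administered on that date".
- **Output.** Descriptive statistics by dosing regimen in the Safety Analysis Population, a by-patient listing, and a split at 80%: "The number and percentages of patients who are <80% compliant" and the complement.

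SAP 4.8 drops only the Phase 2 analyses, so this output is still produced for Phase 1b.

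**The concern.** The two halves of the ratio are in different units. The denominator is in tablets. The numerator for an undisturbed cycle is dosing days times doses per day, and tablets per dose never enters. The two agree only where each dose is a single tablet.

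Read literally, the rule puts patients who took every tablet into the low-compliance category. The artefact also grows with dose, because more tablets per dose enlarge only the denominator. A reader of the table could take the falling percentages for poorer adherence at higher nanatinostat doses, in a study whose purpose is dose finding.

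The rule for flagged dates raises a smaller question. With two doses a day, a date on which only the second was missed still had the first one taken, and the rule scores that first dose as zero.

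**Working it through.** The documents give no compliance figure to reproduce, so the check applies SAP 4.5.2 as written to each level in Protocol Table 4.

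**Inputs.** Tablet strengths are 10 mg and 450 mg (Protocol 5.1.1, 5.2.1; SAP 4.5.2), so a 900 mg valganciclovir dose is 2 tablets. Cycle 1 is 28 days (Protocol 3.1.2). Nanatinostat is dosed on 4 days a week at levels -1 to 7 (16 days) and on 7 days a week at levels 8 to 13 (28 days). As an example of the conversion, level 11 is "30 mg and 30 mg divided dose", which is 3 + 3 tablets. At levels 6 and 7 valganciclovir is 900 mg twice daily for 21 days, after which "subsequent valganciclovir dosing will be reduced to once daily at breakfast". Twice-daily dosing is taken to be divided dosing for both drugs.

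**Numerator check (full adherence, Cycle 1).** Counted = dosing days × doses per day. Expected = dosing days × tablets per day.

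| Level | Nanatinostat tablets per dosing day | Nanatinostat counted/expected | % | Valganciclovir counted/expected | % |
|---|---|---|---|---|---|
| -1 | 1 | 16/16 | 100 | 28/56 | 50.0 |
| 1 | 2 | 16/32 | 50.0 | 28/56 | 50.0 |
| 2 | 3 | 16/48 | 33.3 | 28/56 | 50.0 |
| 3 | 4 | 16/64 | 25.0 | 28/56 | 50.0 |
| 4 | 2+1 | 32/48 | 66.7 | 28/56 | 50.0 |
| 5 | 2+2 | 32/64 | 50.0 | 28/56 | 50.0 |
| 6 | 1+1 | 32/32 | 100 | 49/98 | 50.0 |
| 7 | 2+1 | 32/48 | 66.7 | 49/98 | 50.0 |
| 8 | 2+1 | 56/84 | 66.7 | 56/56 | 100 |
| 9 | 2+2 | 56/112 | 50.0 | 56/56 | 100 |
| 10 | 3+2 | 56/140 | 40.0 | 56/56 | 100 |
| 11 | 3+3 | 56/168 | 33.3 | 56/56 | 100 |
| 12 | 4+3 | 56/196 | 28.6 | 56/56 | 100 |
| 13 | 4+4 | 56/224 | 25.0 | 56/56 | 100 |

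For valganciclovir at levels 6 and 7, counted = 21×2 + 7×1 = 49 and expected = 21×4 + 7×2 = 98. Every entry below 100% is also below 80%. The ratio is doses per day over tablets per day, so the 21-day cycles give the same percentages. Valganciclovir at levels 6 and 7 stays at 50%, because one 2-tablet dose a day gives 21/42.

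**Flagged-date check (tablets counted correctly).** At levels 8 to 13, "the second dose of nanatinostat and valganciclovir will be taken 4 hours later at approximately lunch time on Days 1 to 7". Valganciclovir is 1 + 1 tablets a day, so 56 are expected in 28 days. Suppose only the second dose is missed on *k* dates:

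- actual compliance = (56 − *k*)/56
- compliance under the rule = (56 − 2*k*)/56
- difference = *k*/56, or 1.79 points per date

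With *k* = 6 the values are 50/56 = 89.3% actual and 44/56 = 78.6% under the rule. With *k* = 5 the rule gives 46/56 = 82.1%, still above the cut. With *k* = 12 actual compliance is 44/56 = 78.6%, below the cut either way. The category therefore changes only for 6 to 11 such dates in 28 days. Over three cycles (70 days, 140 tablets), three such dates give 137/140 = 97.9% against 134/140 = 95.7%.

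**The case against.** **The missing factor is a drafting slip that would be caught.** The section speaks of tablets throughout, and in a cycle with no change the number taken should equal the number expected. A result of 25% for every adherent level 13 patient would look odd, and SAP 3.5 requires independent programming and senior review. That is fair as a forecast. But two programmers working from the same sentence can reproduce the same error, and SAP 1 says analyses are described in advance to avoid post hoc decisions. The written rule still gives the wrong number.

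**The flagged-date rule is a choice, not an error.** This largely stands. It is disclosed and conservative, it suits an eCRF entry made by date, and nothing in the documents shows that the database identifies which daily dose was missed. It is right for once-daily dosing and when both doses were missed. It is also right when the first dose is missed and Protocol 5.6.3 is followed, since at levels 4 to 13 dosing then resumes the next day. Its effect per date is small.

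**The reach may be less than the table suggests.** A reader might infer that patients at 12 of 14 nanatinostat levels and 8 of 14 valganciclovir levels will be misreported. The documents do not support that count. Under Table 5, levels -1, 4 and 5 open only after particular toxicity outcomes, and the footnote to Table 4 calls 8, 10 and 12 provisional. The documents do not list which levels enrolled anyone.

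**The net direction is not settled.** A reader might also infer that reported compliance must be too low overall. The denominator covers completed cycles only. If tablets from an unfinished last cycle enter the numerator, compliance rises: at level 9 with tablets counted correctly, one full cycle plus 10 days gives (38×4)/(28×4) = 135.7%. The SAP does not say whether they do.

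**Conclusion.** The numerator for undisturbed cycles is wrong as written. For a fully adherent patient it gives 25.0% to 66.7% for nanatinostat at every level except -1 and 6, and 50% for valganciclovir at levels -1 to 7. Such patients would be placed below 80% at whichever of these levels enrolled patients. This rests on a literal reading of the sentence, with twice-daily dosing treated as divided.

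The flagged-date rule is secondary. It is an acceptable stated convention with a known one-sided error in one situation. The documents give no missed-dose rate, so how often that situation arises is unknown.

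It would be tempting to go further and say that efficacy, safety or dose selection is compromised. The documents do not support that. Compliance feeds no endpoint or analysis set. DLT evaluability has its own 75% rule (Protocol 5.5.2), and RP2D selection does not use this table. Total dose received is summarized separately (SAP 4.6.1), and no formal comparison of regimens is planned (SAP 4.1.1). The consequence is confined to one descriptive table and one listing, so severity is minor.

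**What to change.** In SAP 4.5.2, replace the days-times-two sentence with: tablets taken = sum over administered doses of the dose in mg divided by 10 (nanatinostat) or 450 (valganciclovir). Over a completed, fully adherent cycle this gives 100% for both drugs at every level. It also supplies the formula now missing for cycles with a modified dose. The cost is one derivation changed before database lock, with no new data.

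Optionally, for twice-daily dosing, subtract only the missed dose where the eCRF identifies it. Otherwise keep the present convention and show compliance under the alternative assumption (first dose taken) as a sensitivity. Protocol 5.6 requires all doses to be recorded in the eCRFs, and Protocol 5.9.3.1 has paper diaries recording doses and tablet counts. Whether the database separates the two daily doses is not shown, so the sensitivity is the cheaper route. Protocol 5.6.3 needs no change.

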4.5.3 Primary Efficacy Endpoint Analysis Methods

Counts and percentages for each tumor response category assessed by the Investigator per RECIST v1.1 will be presented by dosing regimen. Separate summaries will also be produced by prior anti-PD-1 treatment exposure. Non-evaluable patients are considered non-responders and will be included in the denominator. ORR estimates, from the first post-baseline assessment, with corresponding binomial 95% confidence intervals using the Clopper-Pearson Exact method will also be presented.

For patients receiving pembrolizumab, the analysis will be repeated using iRECIST.

Results from tumor assessments will be provided in separate listings.

